### **7.6.3 Exploratory Efficacy Analysis**

Subgroup analyses on primary endpoint will be provided for the parameters of age at baseline ( $> 65$  years vs  $\leq 65$  years), sex, and remdesivir or other authorized treatments for COVID-19 use at baseline. The interaction between each mentioned parameter and the treatment effect will be added one at a time into the primary logistic model and the corresponding p-value for that interaction term will be provided.

The impact on efficacy of any new authorized treatments recommended as SoC for COVID-19 during the course of the study will also be evaluated using the same method as above.

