8.3. General Considerations

Continuous variables will be summarized by the standard descriptive statistics: number of patients (n), mean, standard deviation, median, minimum, and maximum. Frequency of patients or events and percentages will be summarized in categorical variables.

Missing values on clinical improvement score will be imputed using Last Observation Carried Forward for a maximum of 1 day at Day 7, 2 days at Day 14, and 4 days at Day 28. For

respiratory failure status, where a patient has died, their status will not be considered missing but will be treated as an observation at each timepoint.

Unless otherwise stated, all regression models will be adjusted for age and remdesivir or other authorized treatments for COVID-19 use at baseline.

Results will be considered statistically significant at one-sided alpha of 0.025, and considered to indicate promising trend at one-sided alpha of 0.2.

Additional information is available in the statistical analysis plan (SAP).

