### 3.3 Exploratory Efficacy Endpoint

To further evaluate the impact of the following parameters on the primary endpoint, the interaction term of treatment and following parameters will be fitted into the primary model one at a time.

- Age, sex, and remdesivir or other authorized treatments for COVID-19 use at baseline.
- Use of any new authorized treatments recommended as SoC for COVID-19 during the course of the study.

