#### 7.6.1 Primary Efficacy Analysis

The proportion of patients from each treatment group who are alive and free of respiratory failure on Day 14 will be summarized and compared using logistic regression, with treatment, remdesivir or other authorized treatments for COVID-19 use at baseline (yes vs no) and age at baseline ( $> 65$  years vs  $\leq 65$  years) as covariates. The p-value for treatment effect will be provided based on the Wald test. P-value based on Fisher's exact test will also be provided. Odds ratio along with its 95% confidence interval will be provided based on the exact method. In addition, the risk difference for the treatment effect and 95% confidence interval will be calculated based on the proportion of patients alive and respiratory failure free in the control group and the estimates of odds ratio, along with its 95% confidence interval.

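### The sex and new-treatment interaction models omit the factor's main effect, so the reported interaction p-value can simply reflect a prognostic difference

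*SAP*

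**What the plan says.** The primary logistic model in SAP 7.6.1 is fitted "with treatment, remdesivir or other authorized treatments for COVID-19 use at baseline (yes vs no) and age at baseline" as covariates. It has no term for sex and none for treatments started during the study.

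SAP 3.3 builds the exploratory analyses on that model: "the interaction term of treatment and following parameters will be fitted into the primary model one at a time". The parameters listed are "Age, sex, and remdesivir or other authorized treatments for COVID-19 use at baseline", followed by use of newly authorised treatments during the study. SAP 7.6.3 repeats the rule ("The interaction between each mentioned parameter and the treatment effect will be added one at a time into the primary logistic model") and states the output: "the corresponding p-value for that interaction term will be provided". For new authorised treatments, the impact "will also be evaluated using the same method as above".

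The protocol does not fill the gap. Section 8.3 says "Unless otherwise stated, all regression models will be adjusted for age and remdesivir or other authorized treatments for COVID-19 use at baseline", which covers only the two factors already in the model. Section 8.4.3 says only that interactions with treatment will be investigated.

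**The concern.** An interaction test asks whether the drug effect differs between levels of a factor. It answers that question only if the model also lets the factor affect outcome directly. Age group and baseline therapy meet this condition. Sex and new treatments do not, because the text adds the product term alone.

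What the resulting p-value tests then depends on how the variables are coded, and the SAP does not state a coding. Subgroup effects and the influence of new standard-of-care treatments are the trial's whole exploratory objective. As written, a factor that merely predicts outcome could be reported as changing the drug effect, and that could mislead the choice of population for a later trial.

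**Working it through.** **The plan's own figure.** The documents give no operating characteristic for the interaction tests, so the design figures were checked first. Information per patient per arm on the log odds ratio is 1/[1/(0.78×0.22) + 1/(0.89×0.11)] = 0.0623. At 87 per arm the critical odds ratio at one-sided 0.2 is exp(−0.8416/√(87×0.0623)) = 0.697, as in protocol 8.1. With both futility rules followed, simulation gives 81% power and cumulative stopping of 5% and 9%, against the stated 80%, 5% and 9%.

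**What the written model estimates.** Let T be treatment (0/1), S the factor (0/1), R baseline therapy and A age group. As written:

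logit(p) = β0 + β1·T + β2·R + β3·A + γ·T·S

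- In the arm with T = 0, S drops out, so both levels of the factor are forced to the same log-odds.
- In the arm with T = 1, the difference between levels is γ. So γ is the factor's effect in that arm, that is, main effect plus interaction.
- With over-parameterised (GLM-type) coding the term has 2 df and tests whether the factor matters in either arm.
- With −1/+1 coding the factor's effect is forced to opposite signs in the two arms. A common main effect then largely cancels, provided the arms carry similar information.

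**Check by formula (0/1 coding, no drug effect, no interaction).** Under these conditions γ is about the factor's log odds ratio in one arm of 87. Take 22% failure (from the plan), 55% male (assumed) and a sex odds ratio of 2 (assumed):

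- Solving 0.55·p_m + 0.45·p_f = 0.22 gives p_m = 0.2715 and p_f = 0.1571.
- SE = √[1/(47.85×0.2715×0.7285) + 1/(39.15×0.1571×0.8429)] = √(1/9.464 + 1/5.183) = 0.546.
- ln 2/SE = 0.693/0.546 = 1.27.
- Rejection at two-sided 0.05 ≈ P(Z > 1.96 − 1.27) ≈ 24–25%.

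The same steps give about 48% for an odds ratio of 3. For a new treatment used by 20% with an odds ratio of 5 they give about 79%.

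**Simulation.** 3,000 trials per row, N = 174, 1:1, 78% placebo response, no true interaction, Wald test at two-sided 0.05 (equivalent to the SAP's one-sided 0.025). Assumed: 55% male, 20% new-treatment use, 50% on baseline therapy, 25% over 65. Planned drug effect means 78% vs 89%, an odds ratio of 2.28. Odds ratios for the factor are for failure. Entries are false-positive percentages.

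| Factor, odds ratio | Drug effect | 0/1, active = 1 | 0/1, placebo = 1 | 2-df | −1/+1 | Main effect fitted |
|---|---|---|---|---|---|---|
| Sex, 1 | none | 4.3 | 4.6 | 4.2 | 5.6 | 5.7 |
| Sex, 1.5 | none | 10.3 | 11.8 | 11.7 | 5.1 | 5.2 |
| Sex, 2 | none | 23.3 | 22.8 | 31.4 | 4.7 | 4.9 |
| Sex, 3 | none | 47.6 | 48.9 | 68.2 | 4.2 | 3.8 |
| Sex, 1.5 | planned | 3.4 | 11.8 | 7.1 | 5.7 | 3.7 |
| Sex, 2 | planned | 7.0 | 22.7 | 19.3 | 6.6 | 3.7 |
| Sex, 3 | planned | 15.6 | 48.5 | 48.6 | 8.9 | 3.0 |
| New treatment, 3 | none | 46.2 | 47.0 | 64.8 | 9.7 | 5.2 |
| New treatment, 5 | none | 77.5 | 77.4 | 93.8 | 11.6 | 5.6 |
| New treatment, 10 | none | 96.8 | 96.4 | 99.8 | 12.7 | 4.7 |
| New treatment, 5 | planned | 60.8 | 77.4 | 88.5 | 19.0 | 4.8 |
| New treatment, 10 | planned | 89.2 | 96.3 | 99.5 | 23.6 | 4.5 |

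Non-converged fits were dropped, at most 324 of 3,000 (sex odds ratio 3 with the planned drug effect). The formula and the simulation agree closely where there is no drug effect.

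**The case against.** The wording may be shorthand. One sentence covers several parameters, two of which already have main effects in the model; nothing forbids adding the others, and many programmers would do so by convention. That is plausible, but two separate SAP sections describe the same model without the main effect, and a pre-specified analysis should not depend on the programmer departing from its text.

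The size is uncertain, and this stands. The documents give no sex effect, sex split, or rate or effect of new-treatment use. At a sex odds ratio of 1.25 the rate is only about 6%. With the planned drug effect and 0/1 coding, the answer turns on which arm is coded 1. Effect coding nearly removes the problem for sex (4–9% above), though it still leaves 10–24% for new treatments.

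The analyses are exploratory. They do not affect the primary test, the sample size or the futility rules, and arm-by-sex results shown alongside could expose a spurious p-value. This limits the importance but does not make the test valid.

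Finally, on-study treatment is a post-randomisation factor. Protocol 7.1.3 has it identified post hoc, and protocol 4.4.3 and 6.2 count its start because of progression as treatment failure. Adding a main effect restores the error rate but does not turn it into a proper subgroup factor. That is a further limitation. It also makes a strong link with outcome plausible, which is where the written model misleads most.

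**Conclusion.** The concern holds. For sex and for new authorised treatments, the model as written lacks the main effect, so the p-value labelled as an interaction can be a test of prognosis. The age and baseline-therapy interactions are correctly specified.

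With no true interaction and no drug effect, a nominal 5% test rejects in 10–12% of trials at a sex odds ratio of 1.5, 23–31% at 2 and 48–68% at 3, under 0/1 or 2-df coding. For a new treatment with an odds ratio of 3 to 10, it rejects in 46% to nearly 100%. The factor odds ratios and prevalences are assumptions, and the result depends on a coding the SAP does not give. The documents also give no direction for any sex effect; the two-sided test is affected either way. This should be corrected, but it bears only on exploratory conclusions.

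**What to change.** In SAP 3.3 and 7.6.3, state that each exploratory model adds to the primary model both the parameter's main effect (where it is not already there) and its interaction with treatment, and that the 1-df test of the interaction is reported. Apply this to sex and to each yes/no variable for a new authorised treatment. For two-level factors the interaction test then no longer depends on the coding or the reference arm.

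It would also help to note beside the new-treatment result that the factor arises after randomisation and may reflect progression, so the interaction is descriptive.

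The cost is one SAP sentence and one extra degree of freedom per affected model. No new data are needed, and the sample size and primary analysis do not change.

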## **7.7 Safety**

### **7.7.1 Extent of Exposure and Compliance**

Duration of exposure will be defined in days as:

(date of last dose – date of first dose) + 1 – off-drug days.

If date of first dose is missing then date of first dose dispensed will be used. If last dose date is missing then date of the last known dose consumed will be used.

Duration of exposure will be listed and summarized using descriptive statistics for each treatment group for the SS. The number and percentage of patients with treatment exposure by study day will be summarized for the SS.

The total number of capsules taken over the study duration will be summarized descriptively for the SS, where the total number of capsules taken is calculated as total number of capsules dispensed (30) – total number of capsules returned.

Percentage compliance is calculated as  $100 * \text{actual number of capsules taken/expected number of capsules taken}$ , where actual number taken is defined as the number dispensed (30) – the number returned and expected number taken is defined as  $2 * (\text{planned last treatment date} - \text{first treatment date} + 1)$ . For patients who completed the study treatment, planned last treatment date is the day 14 date; for patients with treatment early termination due to reasons of adverse event, death, physician decision or sponsor decision, planned last treatment date is the end of treatment date; for patients with treatment early termination due to reasons other

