4.4.2. Hepatic injury or renal impairment

4.4.2.1. *Hepatic injury*

Discontinuation of study treatment for abnormal liver tests should be considered by the investigator when a patient meets one of the conditions outlined in [Figure 2](#) or if the investigator believes that it is in the best interest of the patient.

Figure 2: Stopping Criteria for Liver Injury

Abbreviations: ALT = alanine aminotransferase; INR = international normalized ratio; ULN = upper limit of normal
 Note: INR value is not applicable to patients on anticoagulants.

4.4.2.2. *Renal impairment*

If a patient has renal impairment (creatinine clearance <50 mL/min), treatment should be discontinued.

4.4.3. **Discontinuation of study treatment**

A patient may be discontinued early from study drug treatment (ET of study treatment) for the following reasons:

- Lack of efficacy (e.g. patients who require nonstudy antiviral or anticytokine therapy due to progression of COVID-19), and the investigator's decision. Note: remdesivir or other authorized treatments for COVID-19 is allowed if considered SoC, if started prior to randomization or during the study. Initiation of remdesivir or other authorized treatments for COVID-19 during the study will be considered a treatment failure if started due to progression of disease.
- Adverse event
- Withdrawal by patient (specify reason in the eCRF)
- Lost to follow-up
- Death

- Physician decision (i.e. investigator decision based on protocol deviation, assessment that it is not in the patient's best interest to continue, or other reason [specify reason in the eCRF]).
- Sponsor decision (specify reason in the electronic case report form [eCRF])

No temporary treatment discontinuation is permitted.

Patients who discontinue study treatment prematurely will be asked about the reason(s) for discontinuation and will be asked to continue all assessments up to Day 28. Patients will be educated about the continued scientific importance of their data and encouraged to complete the Day 28 Follow-up/EOS assessments even if they discontinue study treatment prematurely.

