## Statistical Analysis Plan

Sponsor Name: Golden Biotechnology Corporation  
Sponsor Protocol ID: GH Covid-2-001

Covance Study ID: 000000203201

Exclusion Criteria 12	patient requires frequent or prolonged use of systemic corticosteroids ( $\geq 20$ mg of prednisone/day or equivalent for $>4$ weeks) or other immunosuppressive drugs (e.g., for organ transplantation or autoimmune conditions).	Non-Programmable check of the prior medications.
Treatment Compliance	patient with study treatment compliance $<50\%$	Non-Programmable check the study treatment compliance based on drug accountability data.
Prohibited Medication or Therapy	patient has used prohibited medications or therapies documented in the protocol or identified by clinical or medical team	Non-Programmable check of the concomitant medication data.

As defined in the table, all important protocol deviations leading to exclusion from the PPS will be determined non-programmatically from the data. Those criteria which require clinical or medical monitoring interpretation will be reviewed prior to database lock.

All important protocol deviations leading to exclusion from the PPS occurring during the study will be reviewed and approved by Golden Biotechnology Corporation prior to database lock and unblinding. Should additional important protocol deviations leading to exclusion from the PPS, not anticipated at the time of preparing this SAP, be identified during the study (and prior to unblinding) they will be documented in a SAP amendment/Per Protocol Set Identification Plan, other document and included in all relevant protocol deviation reviews and approvals.

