## Statistical Analysis Plan

Sponsor Name: Golden Biotechnology Corporation  
Sponsor Protocol ID: GH Covid-2-001

Covance Study ID: 000000203201

than the ones mentioned above, planned last treatment date is either the day 14 date or the end of study date, whichever occurs first.

Percentage compliance will be summarized descriptively by treatment group for the SS. The number and percentage of compliant patients will be presented for the SS, where compliant is defined as percentage compliance between 80.0% and 120.0% inclusive. The following percentage compliance categories will also be presented:

- <50.0%
- $\geq 50.0\%$  and  $<80.0\%$
- $\geq 80.0\%$  and  $\leq 120.0\%$
- $>120.0\%$

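### The compliance denominator differs by stop reason, so early lack-of-efficacy stops leave the per-protocol set while equally adherent adverse-event stops stay

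*SAP*

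**What the plan says.** SAP 7.7.1 defines percentage compliance as actual over expected capsules: "actual number taken is defined as the number dispensed (30) – the number returned and expected number taken is defined as" twice the number of days from first treatment to the planned last treatment date, inclusive.

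The planned last treatment date depends on why treatment ended:

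- For patients who complete treatment, it is Day 14.
- For early stops because of an adverse event, death, or a decision by the physician or sponsor, "planned last treatment date is the end of treatment date".
- For early stops for any other reason, "planned last treatment date is either the day 14 date or the end of study date, whichever occurs first".

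Protocol 4.4.3 lists the reasons for stopping study drug. One is "Lack of efficacy (e.g. patients who require nonstudy antiviral or anticytokine therapy due to progression of COVID-19"), with the investigator's decision. A separate item is "Physician decision (i.e. investigator decision based on protocol deviation" and similar grounds). Lack of efficacy is not named in SAP 7.7.1, so it falls under any other reason. Under the same protocol section, patients who stop treatment early "will be asked to continue all assessments up to Day 28", so for most of them Day 14 comes before end of study.

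SAP 5.4.1 lists, among the deviations that remove a patient from the PPS, a "patient with study treatment compliance" below 50%, judged from drug accountability. SAP 7.6 names the PPS and mITT as supportive efficacy populations, with ITT primary.

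**The concern.** A per-protocol exclusion for poor compliance should reflect how well the patient followed the regimen while on it. Here two patients with identical intake, each taking every capsule until treatment was stopped, can score very differently because of the reason recorded for the stop. One of the reasons on the unfavourable side is progression of the disease that the trial is trying to prevent.

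SAP 5.4.1 presents its exclusions as protocol deviations. A stop for lack of efficacy is a discontinuation that the protocol provides for, not a deviation. Selecting a supportive efficacy set partly on treatment failure makes agreement or disagreement between the PPS and ITT results harder to interpret.

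**Working it through.** **Inputs.** One capsule twice daily for 14 days, in a kit of 30 (Protocol 5.2). The compliance formula is in SAP 7.7.1 and the PPS threshold of 50% in SAP 5.4.1. Planned rates alive and free of respiratory failure are 89% vs 78%, with 174 patients randomized 1:1, so 87 per arm (SAP 2.2 and 2.3).

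**The plan's own figure.** 2 × 14 + 2 spare = 30 capsules, which matches the kit. The expected count for a full course is 2 × (14 − 1 + 1) = 28.

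**Compliance by stop day.** Assume two capsules a day up to and including the stop day, all unused capsules returned, and follow-up to Day 14 or later.

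| Stop day | Capsules taken | Lack of efficacy: taken/28 | Adverse event, death, physician or sponsor decision: taken/(2 × day) |
|---|---|---|---|
| 1 | 2 | 7.1% (excluded) | 100% (kept) |
| 3 | 6 | 21.4% (excluded) | 100% (kept) |
| 5 | 10 | 35.7% (excluded) | 100% (kept) |
| 6 | 12 | 42.9% (excluded) | 100% (kept) |
| 7 | 14 | 50.0% (kept) | 100% (kept) |
| 10 | 20 | 71.4% (kept) | 100% (kept) |

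The cut falls at 14 capsules: 13/28 = 46.4% is excluded and 14/28 = 50.0% is kept.

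**Illustration of the effect.** The documents do not say how many patients would stop early for lack of efficacy, so the share k of Day 14 failures removed is an assumption. With failure rate f, the PPS failure rate is f(1 − k)/(1 − fk).

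| k, both arms | PPS success, active vs placebo | Risk difference | Odds ratio |
|---|---|---|---|
| 0 | 89.0% vs 78.0% | 11.0 points | 2.28 |
| 10% | 90.0% vs 79.8% | 10.2 points | 2.28 |
| 30% | 92.0% vs 83.5% | 8.5 points | 2.28 |
| 50% | 94.2% vs 87.6% | 6.5 points | 2.28 |

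The odds ratio does not move because removing a share k of failures multiplies the failure odds in each arm by the same (1 − k). Precision does fall. With 87 per arm the expected failures are 9.57 and 19.14, and the unadjusted standard error of the log odds ratio is √(1/77.43 + 1/9.57 + 1/67.86 + 1/19.14) = 0.429, so z = 0.825/0.429 = 1.92. At k = 50% the failures are 4.785 and 9.57, the standard error is 0.584 and z = 1.41.

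With unequal shares the odds ratio becomes 2.28 × (1 − k placebo)/(1 − k active):

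- 25% active and 50% placebo: 2.28 × 0.50/0.75 = 1.52.
- 50% active and 25% placebo: 2.28 × 0.75/0.50 = 3.42.

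**The case against.** The strongest reply concedes the rule and disputes its consequence. Several parts of it stand.

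- **Scale.** The main model is logistic. With equal removal the odds ratio is unchanged, and only the risk difference (also reported under SAP 7.6.1) and precision suffer.
- **Lack of efficacy is not the endpoint.** The protocol's example is a need for other antiviral or anticytokine therapy, whereas the endpoint is death or ventilatory support status on Day 14. A patient stopped on Day 5 may be a Day 14 success, so the rule can remove successes too. The illustration treats every removed patient as a failure.
- **Overlap.** Patients given a prohibited drug leave the PPS anyway under other criteria in SAP 5.4.1. The compliance rule bites mainly on those who stop after receiving an authorized treatment. Such treatment is allowed if standard of care, but counts as treatment failure if started for progression (Protocol 4.4.3 and 6.2). It also bites on those who stop with no prohibited drug.
- **Coding.** A progression stop might be recorded as a physician decision, and the eCRF is not available. This does not remove the problem, because PPS membership would then turn on site coding. Recording it as an adverse event is less likely: Protocol Appendix 1 says that lack of drug effect is not an adverse event. It also exempts COVID-19 hypoxemia or respiratory failure needing ventilatory support from adverse-event reporting unless judged drug-related.
- **Scope.** Stops with 14 or more capsules taken are kept, and a patient who also leaves the study before Day 14 has a shorter denominator and may stay.

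SAP 5.4.1 does not cite 7.7.1. However, 7.7.1 holds the only compliance definition, and its lowest category matches the 50% threshold.

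**Conclusion.** The inconsistency is certain on the text. Under full adherence, a lack-of-efficacy stop before Day 7 (fewer than 14 capsules) leaves the PPS, and the same intake with an adverse-event, death, physician or sponsor stop stays. It affects the supportive PPS only.

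The size is unknown. The figures of 10.2, 8.5 and 6.5 points rest on assumed shares of 10%, 30% and 50%, equal removal in both arms, and every removed patient being a Day 14 failure.

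A reader might infer that the rule always shrinks the treatment effect, or that it makes the PPS worthless as a robustness check. The documents support neither. Equal removal leaves the odds ratio at 2.28, and unequal removal could lower or raise it. Nothing in the plan says how such stops would divide between the arms.

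The change is worth making because the exclusion is outcome-related and easy to remove.

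**What to change.** Before unblinding, add lack of efficacy in SAP 7.7.1 to the reasons for which the planned last treatment date is the end of treatment date. A fully adherent patient stopped for treatment failure then scores 100% and is not treated as non-compliant by the PPS rule. The prohibited-medication exclusion in SAP 5.4.1 is unchanged.

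The cost is one phrase. The PPS keeps some patients with short exposure, including someone who took two capsules and stopped on Day 1, as it already does for adverse-event, death, physician and sponsor stops. Counting to Day 14 for every reason would also remove the asymmetry, but it would score all fully adherent Day 1 to 6 stops at 7.1% to 42.9% and exclude them as non-compliant. Patient withdrawal and loss to follow-up would stay under the existing rule.
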